2.1 Data analysis general information

The planned analyses will be performed by Novartis and/or a designated CRO. SAS version 9.4 or later will be used to perform all data analyses and to generate tables, figures and listings.

There is no planned interim efficacy analysis. Prior to the database lock for the primary analysis, tables and figures aggregated by treatment arm for safety data review by the data monitoring committee or for other reporting activities will be produced by an independent statistician and independent statistical programmers.

For between-treatment comparisons of efficacy endpoints, randomization stratification factor, i.e. cytogenetic response status (MCyR vs no MCyR) at screening, will be included in respective stratified statistical tests.

Data included in the analyses

The analysis data cut-off dates for the planned analyses are:

- Primary analysis: After all randomized patients have been on study treatment for 24 weeks or discontinued earlier, i.e., LPFT + 24 weeks.
- 96-week analysis: After all randomized patients have been on study treatment for 96 weeks or discontinued earlier, i.e., LPFT + 96 weeks
- End of study treatment analysis: 30 days after the EOSt. (Note: After the study treatment period, the assigned study treatment will be made available, may be outside of this study, to patients who in the opinion of the investigators are still deriving clinical benefit.)
- PFS/OS update analysis: 5 years from the date when the last randomized patient received the first study dose (irrespective of treatment switch for patients failing bosutinib).

All statistical analyses will be performed using all data collected in the database up to the respective data cut-off date. All data with an assessment date or event start date (e.g. vital sign assessment date or start date of an adverse event) prior to or on the cut-off date will be included in the analysis. Any data collected beyond the cut-off date will not be included in the analysis and will not be used for any derivations.

All events with start date before or on the respective cut-off date and end date after the respective cut-off date will be reported as ongoing. The same rule will be applied to events starting before or on the respective cut-off date and not having documented end date. This approach applies, in particular, to adverse event and concomitant medication reports. For these events, the end date will not be imputed and therefore will not appear in the listings.

General analysis conventions

Pooling of centers: Unless specified otherwise, data from all study centers will be pooled for the analysis. Due to expected small number of patients enrolled at centers, no center effect will be assessed.

Qualitative data (e.g., gender, race, etc.) will be summarized by means of contingency tables by treatment group; a missing category will be included as applicable. Percentages will be calculated using the number of patients in the relevant population or subgroup as the denominator.

Quantitative data (e.g., age, body weight, etc.) will be summarized by appropriate descriptive statistics (i.e. mean, standard deviation, median, minimum, and maximum) by treatment group. For pharmacokinetics (PK) concentration and parameters descriptive statistics also include coefficient of variation (CV)%, geo-mean and geo-CV%.

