If more than one assessment is assigned to the same time window, the assessment performed closest to the target date will be used for by-visit statistical analyses. If 2 assessments within a visit window are equidistant from the target date, then the average of the 2 assessments will be used. If multiple assessments on the same date, then the the average will be used. Data from all assessments (scheduled and unscheduled), including multiple assessments, will be listed.

Table 2-1 Time windows for molecular response

Assessment	Target day of assessment	Time Interval
Baseline	≤ 1	≤ Day 1 [#]
Week 4	29	Day 2 to day 43
Week 8	57	Day 44 - 71
Week 12	85	Day 72 - 99
Week 16	113	Day 100 to day 141
Week 24	169	Day 142 to day 211
Week k (k=36, 48, ...)	$k \times 7 + 1$	Day $k \times 7 - 40$ – $k \times 7 + 43$

Day 1 = Date of randomization
EOT assessments are mapped to the time points as needed.

Table 2-2 Time windows for cytogenetic response

Assessment	Target day of assessment	Time Interval
Baseline	1	≤ Day 1 [#]
Week 24	169	Day 2 to day 253
Week 48	337	Day 254 to day 421
Week 72	505	Day 422 to day 589
Week 96	673	Day 590 to day 700

Day 1 = Date of randomization
EOT assessments are mapped to the time points as needed.

For PRO data time windows will be defined for descriptive summary by visit and longitudinal data analysis. If more than one assessment is available in the same time window, the assessment closest to the planned date will be considered. If two assessments are obtained with the same time difference compared to the scheduled visit day, the assessment obtained prior to visit will be considered.

Table 2-3 Time windows for PRO: MDASI-CML, EQ-5D-5L, PGIC

Assessment	Target day of assessment	Time Interval
Baseline	1	≤ Day 1 [#]
Week 4	29	Day 2 - 43
Week 8	57	Day 44 - 71
Week 12	85	Day 72 - 99
Week 16	113	Day 100 - 141
Week 24	169	Day 142 - 211
Week 36	253	Day 212 - 295
Week 48	337	Day 296 - 505
Week 96	673	Day 506 - 700

Day 1 = Date of randomization

Table 2-4 Time windows for PRO: WPAI-CML

Assessment	Target day of assessment	Time Interval
Baseline	1	≤ Day 1 [#]
Week 4	29	Day 2 - 57
Week 12	85	Day 58 -127
Week 24	169	Day 128- 253
Week 48	337	Day 254 - 505
Week 96	673	Day 506 - 700

Day 1 = Date of randomization

Here's the general rule for the target day of assessment and time interval: For Week k visit, target day of assessment is defined as $k*7+1$. For the time interval, "Lower limit" = "upper limit

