2.5.5 Sensitivity analyses

The following sensitivity analyses will be performed:

- The CMH chi-square test of MMR rate at 24 weeks will be repeated stratifying by the stratum recorded in the CRF (MCyR vs no MCyR at baseline).
- Due to the COVID-19 (Coronavirus) pandemic, there is a risk that planned hospital visits are cancelled, potentially resulting in missing PCR evaluations. In order to assess the impact of COVID-19 (including potential missing data) on the primary endpoint, the

CMH chi-square test of MMR rate at 24 weeks will be repeated on the FAS excluding the patients with planned 24-week visit (start of study treatment + 161 days) after the start date of COVID-19 epidemic. As per Novartis guidance, the start date, in a given country or region, is being defined as the approximate time point at which, according to the WHO situation reports and the Johns Hopkins database, the number of confirmed COVID-19 infections started to increase significantly (around 100 confirmed cases) and/or governments started to take measures (such as stay-at-home orders) to contain the epidemic, whichever occurred first (China: January 1, 2020; South Korea: February 20, 2020; Japan: February 21, 2020; Italy: February 23, 2020 and Rest of the World: March 1, 2020).

- The CMH chi-square test of MMR rate at 24 weeks will be repeated without the imputation rule used in the main analysis in case of missing PCR evaluations at 24 weeks.

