2.6.4 Handling of missing values not related to intercurrent event

Patients with missing PCR evaluations at 96 weeks will be considered as non-responders. However, if the 96-week PCR evaluation is missing, but both a PCR evaluation at 84 weeks and a PCR evaluation at 108 weeks indicate MMR, the 96-week assessment is imputed as a 'Response', assuming that MMR is maintained between 84 and 108 weeks.

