2.6.5 Sensitivity analysis

- In order to assess the impact of COVID-19 (including potential missing data) on the key secondary endpoint, the CMH chi-square test of MMR rate at 96 weeks will be repeated on the FAS excluding the patients with planned 96-week visit (start of study treatment + 665 days) between the start date of the COVID-19 epidemic (China: January 1, 2020; South Korea: February 20, 2020; Japan: February 21, 2020; Italy: February 23, 2020 and Rest of the World: March 1, 2020) and its end date (to be defined in the future).
- The CMH chi-square test of MMR rate at 96 weeks will be repeated without the imputation rule used in the main analysis in case of missing PCR evaluations at 96 weeks.

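### The 96-week cut-off discards Week 96 PCRs that Table 2-1 still accepts for the last patients enrolled; Week 24 has the same gap, and the COVID-19 visit dates do not match Table 2-1

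*Combined protocol and SAP*

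**What the plan says.** The text is the same in SAP Amendment 3.0 (7 August 2020) and Addendum 1.0 (14 October 2020).

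- **Cut-offs (2.1).** "Primary analysis: After all randomized patients have been on study treatment for 24 weeks or discontinued earlier, i.e., LPFT + 24 weeks". The 96-week analysis is set at "After all randomized patients have been on study treatment for 96 weeks or discontinued earlier, i.e., LPFT + 96 weeks". Data dated "prior to or on the cut-off date will be included in the analysis", and "Any data collected beyond the cut-off date will not be included in the analysis and will not be used for any derivations".
- **Windows (2.1.1, Table 2-1).** Week 24 has target Day 169 and window "Day 142 to day 211". From Week 36 on, the target is Day 7k+1 and the window is Day 7k−40 to Day 7k+43. Day 1 is randomization.
- **Missing PCR (2.5.4, 2.6.4).** The patient is a non-responder. The exception at Week 24 needs MMR at Weeks 16 and 36; at Week 96 it applies if "both a PCR evaluation at 84 weeks and a PCR evaluation at 108 weeks indicate MMR".
- **COVID-19 sensitivity analyses (2.5.5, 2.6.5).** Patients are excluded by the date of the "planned 24-week visit (start of study treatment + 161 days") and of the "planned 96-week visit (start of study treatment + 665 days").

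**The concern.** Table 2-1 decides which PCR counts as the Week 24 or Week 96 result, and it accepts results up to six weeks after the target day. The cut-off closes the data on the target day of the last patient. For the latest enrollees the two rules conflict. A PCR that Table 2-1 would accept falls after the cut-off, is treated as missing, and turns a responder into a non-responder. Whether the same late visit counts then depends on enrolment date. Both formally tested endpoints are affected. The SAP itself expects cancelled visits during the pandemic, and late enrollees are the ones whose Week 24 visits fall latest in calendar time.

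The COVID-19 analyses use a third dating of the same visits, which agrees with Table 2-1 in neither the offset nor the starting date.

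**Working it through.** **Inputs.** Cut-offs from 2.1; windows from 2.1.1; N = 222 (148 + 74) and assumed MMR rates of 15% and 35% from 3.1; a 23-point detectable difference at Week 96 from 3.2. Three inputs are not in the pages available and are assumed: the lag g from randomization to first dose (0–14 days), the accrual pattern, and the fraction f of exposed patients whose only in-window PCR falls after the cut-off (5–30%).

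**1. Reproduce Table 2-1.** Target = 7k+1; upper limit = target + integer part of half the gap to the next target; lower limit = previous upper limit + 1.
- Week 24: target 169; upper 169 + (253 − 169)/2 = 211; lower 141 + 1 = 142.
- Week 96: target 673; upper 673 + (757 − 673)/2 = 715; lower 631 + 1 = 632.
- Week 36 runs from Day 212 to 295, and Week 108 from Day 716 to 799.

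All agree with the table.

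**2. Put the cut-off on the same scale.** For a patient first dosed s days before LPFT, the cut-off falls on study day 7k + 1 + s + g.
- Last patient, g = 0: Day 169 and Day 673, the target days.
- In-window days lost = 42 − s − g, not below zero. For the last patient these are Days 170–211 and 674–715.
- With g = 3 the loss is 39 days; with g = 14 it is 28. It reaches zero when s + g = 42.

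**3. Rescue rule.** The Week 36 and Week 108 windows open on Days 212 and 716, so a PCR in them can precede the cut-off only if s + g ≥ 43. Their target days (253, 757) are reached at s + g = 84. Within about 6 weeks of LPFT rescue is impossible. Between 6 and 12 weeks it needs an early Week 36 or Week 108 PCR.

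**4. Patients exposed.** Uniform accrual: 222 × 42 / (months × 30.4375).

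| Accrual (months) | Patients exposed |
|---|---|
| 12 | 25.5 |
| 18 | 17.0 |
| 24 | 12.8 |
| 30 | 10.2 |

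A second route: the Amendment 2 rationale reports 38 randomized by 29 June 2018. The primary lock had passed by 14 October 2020, so LPFT was no later than 24 weeks before that, 29 April 2020. Uniform accrual of the other 184 over those 670 days gives 184 × 42/670 = 11.5.

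**5. Size.** If n patients are exposed and a fraction f of them lose the PCR in both arms alike, each rate and the difference are multiplied by 1 − nf/222.

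| n | f | PCRs lost | Difference (planned 20.0) | Power (planned 0.903) |
|---|---|---|---|---|
| 12 | 5% | 0.6 | 19.95 | 0.902 |
| 12 | 30% | 3.6 | 19.68 | 0.896 |
| 24 | 30% | 7.2 | 19.35 | 0.889 |

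Power is for the two-proportion test with pooled variance, which also reproduces the plan's 222. Not every lost PCR is a lost responder: of the 3.6, about 2.4 × 0.35 + 1.2 × 0.15 = 1.0 would have been in MMR. At Week 96, a 23-point difference with n = 12 and f = 30% would fall by 23 × 3.6/222 = 0.37 points.

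**6. COVID-19 dates.** First dose + 161 and + 665 days are Days 162 and 666 counted from first dose. Table 2-1 targets are Days 169 and 673 counted from randomization. The gap is 7 − g days: 7 at g = 0, 4 at g = 3, none at g = 7. The 2017 SAP used target days 162–168 for Week 24 (molecular table) and 666–672 for Week 96 (cytogenetic table), so the offsets match the first days of those superseded ranges. A 7-day band holds about 2–4 patients (222 × 7/913 to 222 × 7/365).

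**The case against.** **The cut-off is where it should be.** It equals the Table 2-1 target, and data on that day are included. A reader might infer that the cut-off misses the Week 96 visit; it does not. The conflict is only with the upper window limit. That limit nevertheless decides whether a PCR counts, and it does so for everyone enrolled earlier.

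**Safeguards exist.** Both tests are rerun without the rescue rule, and the end-of-study-treatment analysis has a cut-off at least 30 days later. The first removes the rescue asymmetry but does not restore a late PCR. The second would recover most late Week 96 PCRs, but it is done only if required and without formal testing. The amendment log also says the protocol's imputation rules were updated for unscheduled visits near Weeks 24 and 96. That protocol text is not in the pages available, and 2.1 would still bar data after the cut-off.

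**The COVID-19 offsets may be right.** Table 2-1 is a remapping device, and the protocol visit calendar is not in the pages available. Under the 2017 convention, first dose + 161 days is the first day of Week 24. This stands. A reader might infer that the offsets are 7 days wrong and should be + 168 and + 672; the documents show only that the two sections disagree. The epidemic start dates are themselves approximate.

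**The effect is small and even-handed.** This also stands. The rule applies to both arms alike.

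**Conclusion.** The gap is real and narrow. As written, the rules discard a late but in-window Week 96 PCR for patients first dosed within about 42 days of LPFT, less any lag from randomization to first dose, and count those patients as non-responders. Week 24 has the same gap. About 10–26 patients are exposed under uniform accrual over 12–30 months. With about 12 exposed and 5–30% of them late, 0.6–3.6 PCRs are lost and the planned 20-point difference moves by about 0.1–0.3 points; with 24 exposed and 30% late it moves by about 0.65.

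Two stronger readings do not follow. One is that everyone starting within 12 weeks of LPFT is beyond rescue: between 6 and 12 weeks part of the later window is already open. The other is that the primary test is invalid: the loss is a few PCRs, falls on both arms, and tends to shrink the difference.

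The COVID-19 dating is a separate inconsistency of at most about a week for lags of 0–14 days, confined to sensitivity analyses. The documents do not settle which date is correct. A further copy of the revision history suggests a later SAP version, whose body was not available.

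**What to change.** **Week 96 (2.1).** For the key secondary endpoint, let Week 96 PCRs dated up to Day 715 be used if taken on study treatment and on or before the EOT visit. Alternatively, set the cut-off late enough to close the last patient's Week 96 window (LPFT + 714 days, 102 weeks, at zero lag) with the same on-treatment limit. That limit is needed because study treatment may end at LPFT + 96 weeks. The cost is one exception to the cut-off rule, or up to 6 weeks' delay. The 2017 SAP allowed 30 days after LPFT + 96 weeks for its end-of-study-treatment analysis, so a margin has precedent; 30 days would cover 30 of the 42.

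**Week 24.** The primary database was locked before the addendum. Add only a supplementary rerun at the next data cut that includes Week 24 PCRs up to Day 211, labelled post hoc. The primary result stays as reported.

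**COVID-19 analyses (2.5.5, 2.6.5).** Reconcile the offset and the starting date (first dose or randomization) with the protocol visit calendar and Table 2-1, and state which governs. Label any change to the Week 24 version as post hoc. The Week 96 version can be settled before its lock, when the epidemic end date, still open, is defined.

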2.1.1 General definitions

Investigational drug and study treatment

Investigational drug, will refer to the asciminib only. Whereas, *study treatment* will refer to asciminib or control treatment, i.e. bosutinib, received during the treatment phase. Switched treatment will refer to asciminib received during treatment switch phase.

Treatment arms

- Asciminib (Subjects randomized to asciminib arm at the beginning of the study)
- Bosutinib (Subjects randomized to bosutinib arm at the beginning of the study)

Date of end of study treatment (EOsT)

The EOsT date is the date that the study treatment is ended for the entire study. On this date, patients are treated for at least 96 weeks if they are not eligible to switch study treatment or are treated for at least 48 weeks after they have switched to asciminib treatment, unless patients have discontinued study treatment earlier

Date of first administration of randomized study treatment

The date of first administration of randomized study treatment (FD) is derived as the first date when a non-zero dose of study treatment was administered as per the Dosage Administration Record (DAR) electronic case report form (eCRF). The date of first administration of study treatment will also be referred as *start of study treatment*.

The date of first administration of randomized study treatment is the same as the date of first administration of investigational drug or control drug.

Date of first administration of switched treatment

For subjects switching from bosutinib to asciminib, the date of first administration of switched treatment (FD_{switch}) is derived as the first date when a non-zero dose of asciminib was administered as per the DAR eCRF. The date of first administration of switched treatment (asciminib) will also be referred as *start of switched treatment*.

Date of last administration of randomized study treatment

The date of last administration of randomized study treatment (LD) is defined as the last date when a non-zero dose of study treatment was administered as per DAR eCRF. For subjects switching from bosutinib to asciminib, this includes the dose of bosutinib administered as bridging therapy between their treatment failure and the first dose of asciminib administered.

The date of last administration of randomized study treatment is the same as the date of last administration of investigational drug or control drug.

Date of last administration of switched treatment

The date of last administration of switched treatment (LD_{switch}) is defined as the last date when a non-zero dose of switched treatment (asciminib) was administered as per DAR eCRF.

Study day

The study day, describes the day of the event or assessment date, relative to the reference start date.

The study day is defined as:

- The date of the event (visit date, onset date of an event, assessment date, etc.) – reference start date + 1 if event is on or after the reference start date;
- The date of the event (visit date, onset date of an event, assessment date, etc.) – reference start date if event precedes the reference start date.

The reference start date for safety assessments (e.g. adverse event onset, laboratory abnormality occurrence, vital sign measurement, dose interruption, PK, etc.) is the start of study treatment.

The reference start date for all other, non-safety assessments (e.g. molecular response, survival time, disease progression, ECOG performance status, patient reported outcomes (PRO), etc.) is the date of randomization.

The study day will be displayed in the data listings. If an event starts before the reference start date, the study day displayed on the listing will be negative.

Switch study day

The switch study day, describes the day of the event or assessment date, relative to the start of switched treatment.

Switch study day = date of event - start of switched treatment + 1, if event is on or after the start of switched treatment

Switch study day = date of event - start of switched treatment, if event precedes the start of switched treatment

The switch study day will be displayed in the data listings if an event starts on or after the start of switched treatment.

Time unit

A year length is defined as 365.25 days. A month length is 30.4375 (=365.25/12) days. If duration is reported in months, duration in days will be divided by 30.4375. If duration is reported in years, duration in days will be divided by 365.25.

A week length is defined as 7 days. If duration is reported in weeks, duration in days will be divided by 7.

Baseline for the treatment period

For efficacy evaluations, the last non-missing assessment, including unscheduled assessments on or before the date of randomization is taken as “baseline” value or “baseline” assessment. In

the context of baseline definition, the efficacy evaluations also include PRO and performance status.

For safety evaluations, the last available assessment, including unscheduled assessments before the date of start of study treatment is taken as “baseline” assessment.

For pre-dose electrocardiogram (ECG), the last available assessment before the treatment start date/time is used for baseline.

For ECGs, where study requires multiple replicates per time point, the average of these measurements would be calculated for baseline (if not already available in the database).

For mutations, the Week 1 Day 1 assessment is taken as “baseline” assessment.

In rare cases where multiple laboratory measurements meet the baseline definition, with no further flag or label that can identify the chronological order, then the following rule should be applied: If values are from central and local laboratories, the value from central assessment should be considered as baseline.

If patients have no value as defined above, the baseline result will be missing.

Baseline for the treatment switch period

For subjects switching from bosutinib to asciminib, the last non-missing assessment, including unscheduled assessments before the date of first administration of asciminib is taken as “baseline” assessment for the switched treatment period, and denoted as baseline_switch for short.

On-treatment assessment/event and observation periods

For adverse event reporting the overall observation period will be divided into three mutually exclusive segments for subjects without treatment switching and into up to five mutually exclusive segments for subjects switching treatment:

For subjects without treatment switching:

1. **pre-treatment period:** from day of patient’s informed consent to the day before first administration of study treatment (FD)
2. **on-treatment period:** from date of first administration of study treatment to 30 days after date of last actual administration of study treatment (including start and stop date) (LD). Note: Patients will be treated up to the end of study treatment period (EOsT). This will be the last actual administration of study treatment for each patient if the patient has not discontinued study treatment earlier. On this date, all patients without treatment switching will have been treated for at least 96 weeks unless patients have discontinued study treatment earlier. After this period, the assigned study treatment will be made available, may be outside of this study, to patients who in the opinion of the investigators are still deriving clinical benefit.
3. **post-treatment period:** starting at day 31 after last administration of study treatment.

For subjects with treatment switching from bosutinib to asciminib:

- **pre-treatment period:** from day of patient's informed consent to the day before first administration of study treatment (FD)
- **on-treatment period:** from date of first administration of study treatment to either the day before the first administration of asciminib (FD_{switch}) or 30 days after the date of last actual administration of bosutinib (LD), whichever comes first.
- **post-treatment period:** from day 31 after last administration of bosutinib to the day before the first administration of asciminib (FD_{switch}). If the end date is before the start date, this period is not applicable.
- **on-switched treatment period:** from date of first administration of asciminib (FD_{switch}) to 30 days after date of last actual administration of asciminib (LD_{switch}).
NOTE: Subjects are treated in the study up to end of study treatment period (EOsT). On this date, all subjects with treatment switching will have been treated for at least 48 weeks after switching unless they have discontinued the switched treatment earlier.
- **Post-switched treatment period:** from day 31 after last actual administration of asciminib (LD_{switch}).

If dates are incomplete in a way that clear assignment to pre-, on-, post-, on-switched-, post-switched-treatment period cannot be made, then the respective data will be assigned to the on-treatment period.

Safety summaries (tables, figures) on the Safety set (respectively on the Switch Analysis Set) include only data from the on-treatment (resp. on-switched treatment) period with the exception of baseline data which will also be summarized where appropriate (e.g. change from baseline summaries). In particular, summary tables for adverse events (AEs) will summarize only on-treatment (resp. on-switched treatment) events, with a start date during the on-treatment (resp. on-switched treatment) period (**treatment-emergent** AEs) (resp. switched-treatment-emergent AEs). In addition, a separate summary for death including on-treatment and post-treatment deaths will be provided.

However, all safety data (including those from the pre-treatment, post-treatment and post-switched treatment period) will be listed and flagged as appropriate.

Efficacy summaries on the FAS (apart from OS and PFS) include data from baseline up to either the last assessment on or before the EoT visit or before or on treatment failure, whichever is the earliest.

Efficacy summaries on the Switch Analysis Set include data from baseline_switch up to the last assessment on or before the S-EoT visit or before or on treatment failure during the switched treatment period, whichever is the earliest.

The efficacy assessments collected post-treatment failure, post-EoT or post S-EoT visit are not included in any efficacy analyses (except for OS and PFS analyses). However, they will be listed and flagged as appropriate.

Windows for multiple assessments

Data such as molecular response, cytogenetic response collected over time (including unscheduled visits) will be summarized by scheduled time point. As patients do not always adhere to the visit schedule, visits will be remapped according to visit windows defined in Tables 2-1 to Table 2-4 of this document to enable by-visit analysis. Only those protocol-defined visits will have the visit window defined. Each assessment (including the end of treatment assessment), either scheduled or unscheduled, will have a mapped visit assigned, as long as study day is available, according to the defined visit window up to the date with data included.

If more than one assessment is assigned to the same time window, the assessment performed closest to the target date will be used for by-visit statistical analyses. If 2 assessments within a visit window are equidistant from the target date, then the average of the 2 assessments will be used. If multiple assessments on the same date, then the the average will be used. Data from all assessments (scheduled and unscheduled), including multiple assessments, will be listed.

Table 2-1 Time windows for molecular response

Assessment	Target day of assessment	Time Interval
Baseline	≤ 1	≤ Day 1 [#]
Week 4	29	Day 2 to day 43
Week 8	57	Day 44 - 71
Week 12	85	Day 72 - 99
Week 16	113	Day 100 to day 141
Week 24	169	Day 142 to day 211
Week k (k=36, 48, ...)	$k \times 7 + 1$	Day $k \times 7 - 40$ – $k \times 7 + 43$

Day 1 = Date of randomization
EOT assessments are mapped to the time points as needed.

Table 2-2 Time windows for cytogenetic response

Assessment	Target day of assessment	Time Interval
Baseline	1	≤ Day 1 [#]
Week 24	169	Day 2 to day 253
Week 48	337	Day 254 to day 421
Week 72	505	Day 422 to day 589
Week 96	673	Day 590 to day 700

Day 1 = Date of randomization
EOT assessments are mapped to the time points as needed.

For PRO data time windows will be defined for descriptive summary by visit and longitudinal data analysis. If more than one assessment is available in the same time window, the assessment closest to the planned date will be considered. If two assessments are obtained with the same time difference compared to the scheduled visit day, the assessment obtained prior to visit will be considered.

Table 2-3 Time windows for PRO: MDASI-CML, EQ-5D-5L, PGIC

Assessment	Target day of assessment	Time Interval
Baseline	1	≤ Day 1 [#]
Week 4	29	Day 2 - 43
Week 8	57	Day 44 - 71
Week 12	85	Day 72 - 99
Week 16	113	Day 100 - 141
Week 24	169	Day 142 - 211
Week 36	253	Day 212 - 295
Week 48	337	Day 296 - 505
Week 96	673	Day 506 - 700

Day 1 = Date of randomization

Table 2-4 Time windows for PRO: WPAI-CML

Assessment	Target day of assessment	Time Interval
Baseline	1	≤ Day 1 [#]
Week 4	29	Day 2 - 57
Week 12	85	Day 58 -127
Week 24	169	Day 128- 253
Week 48	337	Day 254 - 505
Week 96	673	Day 506 - 700

Day 1 = Date of randomization

Here's the general rule for the target day of assessment and time interval: For Week k visit, target day of assessment is defined as $k*7+1$. For the time interval, "Lower limit" = "upper limit

of prior applicable visit" +1. "Upper limit" = "target day of current visit" + integer part of ("target day of next applicable visit" – "target day of current visit")/2.

Visit window for the switched treatment period will use the same rules as described above but with Day 1 being the date of first administration of asciminib. Visit name for the switched treatment period will be defined similarly with annotated by beginning with "S-" (e.g. S-Week 4) to differentiate from those used for the randomized treatment period.

Last contact date

The last contact date will be derived for patients not known to have died at the respective analysis data cut-off date using the last complete date among the following:

Table 2-5 Last contact date data sources

Source data	Conditions
Date of randomization	No condition
Last contact date/last date patient was known to be alive from Survival Follow-up page	Patient status is reported to be alive, lost to follow-up or unknown
Start/End dates from further antineoplastic therapy	Non-missing medication/procedure term
Start/End dates from drug administration record	Non-missing dose. Doses of 0 are allowed
End of treatment date from end of treatment page	No condition
Any specific efficacy (molecular or cytogenetic) assessment date if available	Evaluation is marked as 'done'
Laboratory/PK collection dates	Sample collection marked as 'done'
Vital signs date	At least one non-missing parameter value
Performance status date	Non-missing performance status
Start/End dates of AE	Non-missing verbatim term

The last contact date is defined as the latest complete date from the above list on or before the respective data cut-off date. The cut-off date will not be used for last contact date, unless the patient was seen or contacted on that date. No date post the cut-off date will be used. Completely imputed dates (e.g. the analysis data cut-off date programmatically imputed to replace the missing end date of a dose administration record) will not be used to derive the last contact date.

The last contact date will be used for censoring of patients in the analysis of overall survival.

